### **10.5.2 Safety**

The assessment of safety will be based mainly on the frequency of adverse events and on the number of laboratory values that fall outside of pre-determined ranges. Other safety data (e.g. electrocardiogram, vital signs, and special tests) will be considered as appropriate. Adverse events will be summarized by presenting, for each treatment group, the number and percentage of patients having any adverse event, having an adverse event in each body system and having each individual adverse event. Any other information collected (e.g. severity (CTCAE) or relatedness to study medication) will be listed as appropriate.

#### **Adverse events/infections**

Data collected by AE CRFs and by Infection CRFs will be coded using MedDRA. The number of AE/patients with AE will be summarized by MedDRA system organ class and preferred term. Additionally, AE will be summarized by maximum severity, and for AE with suspected drug relation, serious AE (SAE), and AE leading to permanent discontinuation of study drug. In addition to being analyzed together with AE data, the incidence of bacterial, viral and fungal infections will be tabulated separately for all infections, by maximum severity, for infections with suspected drug relation, serious infections and infections leading to premature discontinuation of study drug. These summary tables will include adverse events of special interest, such as New Onset of Diabetes Mellitus (NODM, for definition see [Section 7.6.4](#)), *de novo* HCC malignancies, HCV- and HCC-related fibrosis.

All information pertaining to AE noted during the study will be listed by treatment group and patient, detailing the verbatim term given by the investigator, MedDRA preferred term and system organ class, start/end dates, severity, seriousness, relationship to study drug and action taken. The AE onset will also be shown relative (in number of days) to the date of initial dose.

AE starting before, or 28 or more days after the discontinuation of study medication, will not be considered as treatment-emergent and will not be included in AE/infection summary tables but listed only.

## **Laboratory data**

Abnormalities according notable criteria (see [Appendix 2](#)) will be identified. The proportions of patients with clinically notable abnormalities according to the notable criteria will be summarized. Shifts from baseline value to worst post-baseline value based on the normal ranges will be presented graphically ([Amit et al., 2008](#)). The worst observation is defined as the highest or lowest measure during the different observations periods whereby high or low are chosen according to the direction of abnormality. Descriptive statistics of absolute values as well as change from baseline of all laboratory variables will be presented by visit and treatment group. A by-patient listing of all clinically notable abnormal laboratory data will be generated. Only assessments obtained up to 28 days after the discontinuation of study medication will be considered “on-treatment” and analyzed with relationship to immunosuppressive therapy.

### **10.5.3 Tolerability**

Tolerability of the study drug will be assessed from the rate of patients who withdraw prematurely from study drug or in whom study drug had to be converted to another immunosuppressive regimen due to abnormal laboratory results or adverse events. The frequency distribution of these reasons will be presented and compared between the treatments.

### **10.5.4 Resource utilization**

Not applicable. No resource utilization data will be generated.

### **10.5.5 Health-related Quality of Life**

Not applicable. No health-related quality of life data will be generated.

### **10.5.6 Pharmacokinetics**

Everolimus C0-h whole blood levels will be summarized by visit using descriptive statistics. Tacrolimus C0-h whole blood levels will be summarized by visit and treatment group using descriptive statistics.

### **10.5.7 Pharmacogenetics/pharmacogenomics**

Not applicable. No pharmacogenetic/pharmacogenomic data will be generated.

### **10.5.8 Biomarkers**

HCV viral load (HCV-ribonucleic acid (RNA) levels overall and by genotype) will be summarized descriptively by visit and treatment group.

The number of patients with deviations from the therapeutic window will be counted and tabulated separately by visit and in total.

### **10.5.9 PK/PD**

Not applicable. No PK/PD data will be generated.

## **10.6 Interim analysis**

Not applicable. No interim analysis is planned for this trial.

## **10.7 Sample size calculation**

The trial tests the null hypothesis that there is no difference in renal function, estimated by cGFR according to the MDRD-4 formula, at 12 months after randomization between the everolimus-based tacrolimus-minimization regimen and the tacrolimus-based control regimen versus the alternative hypothesis that the difference is 7.0 ml/min/1.73m^2. A sample size of 105 in each group will have 80% power to detect a difference in means of 7.0 ml/min/1.73m^2 assuming that the common standard deviation is 18.0 ml/min/1.73m^2 with a 5% two-sided significance level. (One will decide in favor of H1 when the difference in means would be 5.1 ml/min/1.73m^2 or greater in favor of the everolimus-based group.) To adjust the sample size for a common drop-out rate (DOR) of 20% (using the formula  $N_{adj}=N/(1-DOR)^2$ ), 165 patients need to be randomized per group. Sample sizes were estimated using NQuery (Version 6.1) procedure “Two-group *t*-test for equal means (equal n’s)”.

## **10.8 Power for analysis of critical secondary variables**

Not applicable. Power for the analysis of critical secondary variables was not investigated.

## **11 Discussion and rationale for study design features**

The evaluation of the efficacy and safety of an immunosuppressive regimen in liver transplant recipients is best investigated using a randomized control trial, as opposed to observational studies where confounding by indication cannot be fully accounted for by adjusting by multivariate procedures for differences in confounders that are imbalanced at the time of transplantation. This protocol will not utilize procedures to blind investigators or subjects to treatment assignment. The duration of experience of liver transplant physicians with tacrolimus indicates that optimizing the safety of this medication requires the physician to be aware of the use of tacrolimus and to the trough levels. This open label study, however, does include prospective collection of assessments that relate to potential issues that may be impacted by an open label design, e.g. management of tacrolimus levels above or below target ranges. Importantly, the occurrence of the primary endpoints of this study are objectively measured – renal function by laboratory data, and death or graft survival.

The choice of the control arm for this study is based upon the predominance of tacrolimus use in liver transplantation worldwide in combination with corticosteroids, which are eliminated sometime after the first several months post-transplantation. As opposed to renal transplantation where triple or quadruple therapy is standard, adjunctive therapy with MMF is not pervasive and tends to be used short-term to allow a slow increase in the tacrolimus level while renal function recovers. The present study requires the discontinuation of MMF prior to randomization so that the control group is reflective of a regimen that has an approved liver transplant indication.

## 13 Appendices

### 13.1 Appendix 1: Administrative procedures

#### Regulatory and ethical compliance

This clinical study was designed and shall be implemented and reported in accordance with the ICH Harmonized Tripartite Guidelines for Good Clinical Practice, with applicable local regulations (including European Directive 2001/20/EC, US Code of Federal Regulations Title 21, and Japanese Ministry of Health, Labor, and Welfare), and with the ethical principles laid down in the Declaration of Helsinki.

#### Responsibilities of the investigator and IRB/IEC/REB

The protocol and the proposed informed consent form must be reviewed and approved by a properly constituted Institutional Review Board/Independent Ethics Committee/Research Ethics Board (IRB/IEC/REB) before study start. Approval letters concerning protocol and informed consent will be filed by Novartis. Prior to study start, the investigator is required to sign a protocol signature page confirming his/her agreement to conduct the study in accordance with these documents and all of the instructions and procedures found in this protocol and to give access to all relevant data and records to Novartis monitors, auditors, Novartis Clinical Quality Assurance representatives, designated agents of Novartis, IRBs/IECs/REBs, and regulatory authorities as required. If an inspection of the clinical site is requested by a regulatory authority, the investigator must inform Novartis immediately that this request has been made.

#### Informed consent

Eligible patients may only be included in the study after providing written, IRB/IEC/REB-approved informed consent.

Informed consent must be obtained before conducting any study-specific procedures (i.e., all of the procedures described in the protocol). The process of obtaining informed consent should be documented in the patient source documents.

Novartis will provide to investigators in a separate document a proposed informed consent form that complies with the ICH GCP guideline and regulatory requirements and is considered appropriate for this study. Any changes to the proposed consent form suggested by the investigator must be agreed to by Novartis before submission to the IRB/IEC/REB, and a copy of the approved version must be provided to the Novartis monitor after IRB/IEC/REB approval.

#### Amendments to the protocol

Any change or addition to the protocol can only be made in a written protocol amendment that must be approved by Novartis, Health Authorities where required, and the IRB/IEC/REB. Only amendments that are required for patient safety may be implemented prior to IRB/IEC/REB approval. Notwithstanding the need for approval of formal protocol amendments, the investigator is expected to take any immediate action required for the safety of any patient included in this study, even if this action represents a deviation from the

protocol. In such cases, Novartis should be notified of this action and the IRB/IEC/REB at the study site should be informed within 10 working days.

### **Discontinuation of the study**

Novartis reserves the right to discontinue this study under the conditions specified in the clinical trial agreement.

### **Study drug supply and resupply, storage, and tracking**

Study drugs must be received by a designated person at the study site, handled and stored safely and properly, and kept in a secured location to which only the investigator and designated assistants have access. Upon receipt, all study drugs should be stored according to the instructions specified on the drug labels. Clinical supplies are to be dispensed only in accordance with the protocol.

Medication labels will be in and comply with the legal requirements of Germany. They will include storage conditions for the drug, but no information about the patient except for the randomization number.

The investigator must maintain an accurate record of the shipment and dispensing of study drug in a drug accountability ledger. Monitoring of drug accountability will be performed by the field monitor during site visits and at the completion of the trial. Patients will be asked to return all unused study drug and packaging at the end of the study or at the time of study drug discontinuation.

At the conclusion of the study and as appropriate during the course of the study, the investigator will return all used and unused study drug, packaging, drug labels, and a copy of the completed drug accountability ledger to the Novartis monitor or to the Novartis address provided in the investigator folder at each site.

## 13.2 Appendix 2: Clinically notable laboratory values and vital signs

Laboratory variable	Standard units	SI units
Liver function and related variables		
SGOT (AST)	$\geq 3 \times$ ULN	$\geq 3 \times$ ULN
SGPT (ALT)	$\geq 3 \times$ ULN	$\geq 3 \times$ ULN
Bilirubin	$\geq 3 \times$ ULN	$\geq 3 \times$ ULN
Renal function, metabolic and electrolyte variables		
Urea	None	None
Creatinine	Day 8 or after: $>30\%$ above value from preceding visit or Day 8 to Wk 4: $\geq 4$ mg/dL, After Wk 4: $\geq 3$ mg/dL	Day 8 or after: $>30\%$ above value from preceding visit or Day 8 to Wk 4: $\geq 354$ $\mu\text{mol/L}$ , After Wk 4: $\geq 265$ $\mu\text{mol/L}$
Uric acid	M $\geq 12$ mg/dL F $\geq 9$ mg/dL	M $\geq 714$ $\mu\text{mol/L}$ F $\geq 535$ $\mu\text{mol/L}$
Glucose	<45 mg/dL $>250$ mg/dL	<2.5 mmol/L $>13.9$ mmol/L
Cholesterol	$\geq 350$ mg/dL	$\geq 9.1$ mmol/L
Triglycerides	$\geq 750$ mg/dL	$\geq 8.5$ mmol/L
CPK (MB)	None	None
Potassium	$\leq 3.0$ mEq/L $\geq 6.0$ mEq/L	$\leq 3$ mmol/L $\geq 6$ mmol/L
Calcium	$\leq 6$ mg/dL $\geq 13$ mg/dL	$\leq 1.5$ mmol/L $\geq 3.2$ mmol/L
Hematology variables		
Hemoglobin	<7 g/dL	<4.39 mmol/L
Platelets (thrombocytes)	$<50$ k/mm  $\geq 700$ k/mm 	$<50 \times 10^9$ /L $\geq 700 \times 10^9$ /L
Leukocytes (WBCs)	$\leq 2.0$ k/mm  $\geq 16$ k/mm 	$\leq 2.0 \times 10^9$ /L $\geq 16 \times 10^9$ /L
Hematology variables: differential		
Granulocytes (poly, neutrophils)	$\leq 1,000$ /mm 	$\leq 1 \times 10^9$ /L
Eosinophils	$\geq 12\%$	$\geq 12\%$
Lymphocytes	$\leq 1,000$ /mm 	$\leq 1 \times 10^9$ /L

### Harmonized notable vital signs (and weight)

Vital sign variables	Notable criteria
Pulse (beats/min.)	None
Systolic BP (mm/Hg)	Either an increase of $\geq 30$ that results in $\geq 180$ or $>200$ (mm/Hg) or Either a decrease of $\geq 30$ that results in $\leq 90$ or $<75$ (mm/Hg)
Diastolic BP (mm/Hg)	Either an increase of $\geq 20$ that results in $\geq 105$ or $>115$ (mm/Hg) or Either a decrease of $\geq 20$ that results in $\leq 50$ or $<40$ (mm/Hg)
Weight (Kg)	None

### 13.3 Appendix 3: Possible drug interactions

During treatment with immunosuppressive agents such as everolimus and tacrolimus vaccination may be less effective. The use of live vaccines should be avoided.

#### Possible Everolimus Drug Interactions

Everolimus is mainly metabolized by CYP3A4 in the liver and to some extent in the intestinal wall and is a substrate for the multi-drug efflux pump, P-glycoprotein. Therefore, absorption and subsequent elimination of systemically absorbed everolimus may be influenced by medicinal products that affect CYP3A4 and/or P-glycoprotein. Concurrent treatment with strong 3A4-inhibitors and inducers is not recommended. See also drugs known to interact with tacrolimus (see Appendix 4). Grapefruit and grapefruit juice have the potential to affect the metabolism of drugs metabolized by CYP450 enzymes. Caution should be used in patients being administered everolimus.

Drugs not allowed	Sirolimus	Patients to be discontinued from everolimus if these immunosuppressive drugs are given
	Terfenadine Astemizole Cisapride	Inhibitors of P-450 (CYP), in particular CYP3A (as everolimus) have the potential to increase the exposure to these drugs, resulting in prolongation of QT intervals on ECGs
	Rifampicin Rifabutin	Strong inducers of P-450 (CYP) have the potential to decrease the exposure of everolimus
	Clarithromycin Telithromycin Ritonavir	Strong inhibitors of P-450 (CYP) have the potential to increase the exposure of everolimus
	Itraconazole** Voriconazole** Fluconazole** Ketoconazole**	Strong inhibitors of P-450 (CYP) have the potential to increase the exposure of everolimus
	Cerivastatin Rosuvastatin	Insufficient data available to make recommendations regarding concomitant use of the newer statins and everolimus
	Lovastatin* Simvastatin*	Confirmed interaction between these drugs and drugs which are CYP3A substrates and/or inhibitors
Drugs strongly discouraged	Quinidine Fluoxetine Paroxetine	Potential interaction of everolimus with CYP 2D6 substrates
Drugs necessitating close monitoring	Digoxin	Potential interaction with everolimus has not been evaluated, patients on digoxin should have periodic measurements of digoxin levels

\*Patients requiring treatment with this class of medication should be monitored closely for signs of rhabdomyolysis, such as, dark-colored urine, fever, muscle cramps, pain, spasm, or stiffness, unusual tiredness or weakness.

\*\*Concomitant administration of everolimus and these drugs necessitates close monitoring of everolimus levels. Fluconazole may pose the smallest risk for drug drug-interaction.

## 13.4 Appendix 4: Tacrolimus drug interactions

### Drug interactions

Due to the potential for additive or synergistic impairment of renal function, care should be taken when administering Tacrolimus with drugs that may be associated with renal dysfunction. These include, but are not limited to, aminoglycosides, amphotericin B, and cisplatin.

### Drugs that may alter tacrolimus concentrations

Since Tacrolimus is metabolized mainly by the CYP3A enzyme systems, substances known to inhibit these enzymes may decrease the metabolism or increase bioavailability of Tacrolimus as indicated by increased whole blood or plasma concentrations. Drugs known to induce these enzyme systems may result in an increased metabolism of Tacrolimus or decreased bioavailability as indicated by decreased whole blood or plasma concentrations. Monitoring of blood concentrations and appropriate dosage adjustments are essential when such drugs are used concomitantly.

### \*Drugs that may increase Tacrolimus blood concentrations

Calcium Channel Blockers	Antifungal Agents	Macrolide Antibiotics
Diltiazem	clotrimazole	clarithromycin
nicardipine	fluconazole	erythromycin
nifedipine	itraconazole	troleandomycin
verapamil	ketoconazole**	
	voriconazole	
Gastrointestinal Prokinetic Agents	Other Drugs	
Cisapride	bromocriptine	
metoclopramide	chloramphenicol	
	cimetidine	
	Cyclosporin A	
	danazol	
	ethinyl estradiol	
	methylprednisolone	
	lansoprazole***	
	omeprazole	
	protease inhibitors	
	nefazodone	
	magnesium-aluminum hydroxide	

\*\*In a study of 6 normal volunteers, a significant increase in Tacrolimus oral bioavailability ( $14\pm5\%$  vs.  $30\pm8\%$ ) was observed with concomitant ketoconazole administration (200 mg).

The apparent oral clearance of Tacrolimus during ketoconazole administration was significantly decreased compared to Tacrolimus alone ( $0.430 \pm 0.129$  L/hr/kg vs.  $0.148 \pm 0.043$  L/hr/kg). Overall, IV clearance of Tacrolimus was not significantly changed by ketoconazole co-administration, although it was highly variable between patients.

\*\*\* Lansoprazole (CYP2C19, CYP3A4 substrate) may potentially inhibit CYP3A4-mediated metabolism of Tacrolimus and thereby substantially increase Tacrolimus whole blood concentrations, especially in transplant patients who are intermediate or poor CYP2C19 metabolizers, as compared to those patients who are efficient CYP2C19 metabolizers.

**\*Drugs that may decrease Tacrolimus blood concentrations**

Anticonvulsants	Antimicrobials
carbamazepine phenobarbital phenytoin	rifabutin caspofungin rifampin
Herbal Preparations	Other Drugs
St. John's Wort	sirolimus

\*This table is not all inclusive.

St. John's Wort (*Hypericum perforatum*) induces CYP3A4 and P-glycoprotein. Since Tacrolimus is a substrate for CYP3A4, there is the potential that the use of St. John's Wort in patients receiving Tacrolimus could result in reduced Tacrolimus levels.

In a single-dose crossover study in healthy volunteers, co-administration of Tacrolimus and magnesium-aluminum-hydroxide resulted in a 21% increase in the mean Tacrolimus AUC and a 10% decrease in the mean Tacrolimus Cmax relative to Tacrolimus administration alone.

In a study of 6 normal volunteers, a significant decrease in Tacrolimus oral bioavailability ( $14 \pm 6\%$  vs.  $7 \pm 3\%$ ) was observed with concomitant rifampin administration (600 mg). In addition, there was a significant increase in Tacrolimus clearance ( $0.036 \pm 0.008$  L/hr/kg vs.  $0.053 \pm 0.010$  L/hr/kg) with concomitant rifampin administration.

Interaction studies with drugs used in HIV therapy have not been conducted. However, care should be exercised when drugs that are nephrotoxic (e.g., ganciclovir) or that are metabolized by CYP3A (e.g., nelfinavir, ritonavir) are administered concomitantly with Tacrolimus. Based on a clinical study of 5 liver transplant recipients, co-administration of Tacrolimus with nelfinavir increased blood concentrations of Tacrolimus significantly and, as a result, a reduction in the Tacrolimus dose by an average of 16-fold was needed to maintain mean trough Tacrolimus blood concentrations of 9.7 ng/mL. Thus, frequent monitoring of Tacrolimus blood concentrations and appropriate dosage adjustments are essential when

nelfinavir is used concomitantly. Tacrolimus may affect the pharmacokinetics of other drugs (e.g., phenytoin) and increase their concentration. Grapefruit juice affects CYP3A-mediated metabolism and should be avoided (see Dosage Administration).

Following co-administration of Tacrolimus and sirolimus (2 or 5 mg/day) in stable renal transplant patients, mean Tacrolimus AUC0-12 and Cmin decreased approximately by 30% relative to Tacrolimus alone. Mean Tacrolimus AUC0-12 and Cmin following co-administration of 1 mg/day of sirolimus decreased approximately 3% and 11%, respectively. The safety and efficacy of Tacrolimus used in combination with sirolimus for the prevention of graft rejection has not been established and is not recommended.

### 13.5 Appendix 5: Guidelines for everolimus dose reduction

An investigator may interrupt temporarily or reduce the dosage of everolimus, if in his/her opinion this is clinically warranted, in response to any causally associated AE (e.g., neutropenia, thrombocytopenia, leukocytopenia, hyperlipidemia, hypertriglyceridemia). The following guidelines should be followed:

#### 1- PLATELETS

Platelet count < 75,000/mm^3

Step 1: dose reduction should be considered and the first dose reduction may be instituted at the discretion of the Investigator.

Step 2: if the platelet count remains below 75,000/mm^3 despite the initial dose reduction, a further dose reduction may be implemented per the table below.

Platelet count < 50,000/mm^3 Dose interruption should be considered.

Platelet count < 30,000/mm^3 Dose interruption will be mandatory.

If the platelet count returns to 50,000/mm^3 for 3 days, everolimus may be restarted at lowest reduced dose. If the platelet count is stable at the reduced dose for 3 days, everolimus may be increased to the next higher dose. If the platelet count remains stable at greater than 75,000/mm^3 for 7 days, the full dose of everolimus may be restarted.

#### 2- HEMOGLOBIN

Hemoglobin < 8 g/dL

Step 1: dose reduction should be considered and the first dose reduction may be instituted at the discretion of the Investigator.

Step 2: if the hemoglobin remains below 8 g/dL despite the initial dose reduction, a further dose reduction may be implemented per the table below.

Hemoglobin < 6 mg/dL: dose interruption will be mandatory.

Once hemoglobin returns to > 6 mg/dL for 3 days, everolimus may be restarted at the lowest (one

tablet b.i.d) level. If the hemoglobin is stable at the reduced dose for 3 days, everolimus may be increased to the next higher dose. Once hemoglobin returns to levels > 8 mg/dL for 7 days, everolimus may be increased to the full dose.

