#### **Exclusion Criteria - Randomization**

1. Patients who are not able to take oral medication at time of randomization.
2. Patients with platelet count <50,000/mm^3)
3. Patients with an absolute neutrophil count of <1,000/mm^3
4. Patients with a white blood cell count of <2,000/mm^3)
5. Patients with hemoglobin < 6.0 g/dL.(transfusion of erythrocytes concentrate during or after transplantation are allowed according to investigator discretion.)
6. Patients with uncontrolled hypercholesterolemia (>350mg/dL; >9mmol/L) or hypertriglyceridemia (>750 mg/dL, >8.5 mmol/L).
7. Patients with a protein/creatinine ratio indicating daily urinary protein excretion >1 g/24h at time of randomization.
8. Patients with clinically significant or uncontrolled systemic infection requiring active use of IV antibiotics at the time of randomization.

9. Patients who have received an investigational drug within 30 days prior to randomization.

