#### 3- WHITE BLOOD CELLS

WBC < 3,000/mm^3

**Step 1:** dose reduction should be considered and the first dose reduction may be instituted at the discretion of the Investigator.

**Step 2:** if the white count remains below 3,000/mm^3 despite the initial dose reduction, a further dose reduction may be implemented per the table below.

WBC < 1,500/mm^3: dose interruption will be mandatory.

Once WBC returns to 1,500/mm^3 for 3 days, everolimus may be restarted at the lowest (one tablet b.i.d) level. If the WBC is stable at the reduced dose for 3 days, everolimus may be increased to the next higher dose. Once WBC returns to levels > 3,000/mm^3 for 7 days, everolimus may be increased to the full dose.

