#### **Everolimus dose reduction**

	Platelet count (/mm  )	Hemoglobin (g/dL)	WBC count (/mm  )	Cholesterol (mmol/L)	Triglycerides (mmol/L)
Dose reduction	<75,000	<8	<3000	> 8	>6.5
Interruption	<30,000	<6	<1500	>9	>8.5

An investigator may interrupt temporarily or reduce, the dosage of the investigational drug (everolimus), if in his/her opinion this is clinically warranted.

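### Appendix 5 prints three haemoglobin thresholds for everolimus (mandatory interruption, restart, full dose) in mg/dL instead of g/dL; the restart and full-dose rules are stated nowhere else

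*Protocol*

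**What the plan says.** Protocol Appendix 5 (section 13.5) sets out when everolimus is to be reduced, interrupted, restarted and returned to full dose. Section 6.6.3 refers investigators to it for several laboratory changes, a fall in haemoglobin among them, and the appendix says its guidelines should be followed.

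The haemoglobin subsection gives five limits. The first two, for dose reduction, are in g/dL: below 8 g/dL for Step 1, and for Step 2 "if the hemoglobin remains below 8 g/dL despite the initial dose reduction". The other three are in mg/dL:

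- Interruption: "Hemoglobin < 6 mg/dL: dose interruption will be mandatory".
- Restart at the lowest level: "Once hemoglobin returns to > 6 mg/dL for 3 days".
- Full dose: "Once hemoglobin returns to levels > 8 mg/dL for 7 days, everolimus may be increased to the full dose".

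The summary table later in Appendix 5 has a haemoglobin column headed in g/dL, with two rows: dose reduction below 8 and interruption below 6.

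**The concern.** The unit changes partway through one short set of rules for one laboratory value. The three limits after the change are the safety decisions: when the drug must stop, when it may restart and when the full dose may resume. A limit of 6 mg/dL has no clinical meaning for haemoglobin. Taken at face value, the rule would never stop the drug and would never hold back a restart. The summary table can correct a reader on interruption only, because it does not cover restart or full dose.

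**Working it through.** No sample size or power figure is involved. The check is a unit conversion and a comparison of every haemoglobin limit in the protocol.

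**Conversion.** 1 g = 1000 mg, so 6 mg/dL = 6/1000 = 0.006 g/dL and 8 mg/dL = 8/1000 = 0.008 g/dL.

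**Haemoglobin limits, by source.**

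| Source | Rule | Printed limit |
|---|---|---|
| Appendix 5, haemoglobin | Reduction, Step 1 | < 8 g/dL |
| Appendix 5, haemoglobin | Reduction, Step 2 | below 8 g/dL |
| Appendix 5, haemoglobin | Mandatory interruption | < 6 mg/dL |
| Appendix 5, haemoglobin | Restart, after 3 days | > 6 mg/dL |
| Appendix 5, haemoglobin | Full dose, after 7 days | > 8 mg/dL |
| Appendix 5, table | Reduction | < 8 g/dL |
| Appendix 5, table | Interruption | < 6 g/dL |
| Section 5.1, randomization exclusion 5 | Not eligible | < 6.0 g/dL |
| Appendix 2 | Clinically notable | < 7 g/dL |

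Three of the five limits in the haemoglobin subsection are in mg/dL. Every other haemoglobin limit in the table above is in g/dL, including "Patients with hemoglobin < 6.0 g/dL" among the randomization exclusions.

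**Literal reading.** Take an illustrative haemoglobin of 5 g/dL, which is 5 × 1000 = 5,000 mg/dL. It is not below 6 mg/dL, so the mandatory interruption does not apply. It is above both 6 and 8 mg/dL, so the restart and full-dose conditions are met. The same holds for any realistic value.

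**Parallel rule.** The white-cell subsection is built the same way. Its restart value equals its interruption value (1,500/mm³), and its full-dose value equals its reduction value (3,000/mm³). The haemoglobin numbers fit that pattern (restart 6 = interruption 6, full dose 8 = reduction 8) only if all of them are in g/dL. The platelet subsection follows it only in part: full dose matches reduction at 75,000/mm³, but restart is at 50,000/mm³ and mandatory interruption is below 30,000/mm³. The white-cell rule therefore supports g/dL without proving it. The platelet rule also shows that a restart value cannot safely be read off the table's interruption row.

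**After correction.** Interruption below 6 g/dL and reduction below 8 g/dL agree with the table. Restart above 6 g/dL and full dose above 8 g/dL then fit the limits around them.

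**The case against.** The strongest reply is that nobody would be misled. The same subsection gives 8 g/dL twice, the table in the same appendix is headed in g/dL and lists interruption below 6, and section 5.1 and Appendix 2 agree. Restart above 6 and full dose above 8 are simply the other side of the interruption and reduction limits, so the numbers can be recovered. Other text also protects patients. Section 6.6.3 calls for interruption in severe haematologic adverse events, Appendix 5 allows interruption at the investigator's judgement, and restart and full dose are permitted, not required.

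Most of this stands, and it is why the point is minor. It does not make the text right. For haemoglobin, the statement that interruption is mandatory is attached only to the mg/dL sentence, and the restart and full-dose rules appear only in mg/dL.

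One limit on relevance should also be granted. Exclusion 5 allows patients with haemoglobin from 6.0 to 8 g/dL to be randomized. At entry, those below 8 g/dL meet only the reduction limit, which is printed correctly. The misprinted limits come into play only if haemoglobin falls further, or at the later steps of restart and return to full dose.

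**Conclusion.** The error is real and in the current protocol text. Three of five haemoglobin limits in the Appendix 5 subsection are printed 1000 times too low. One of them, interruption, is given correctly in the table; the other two, restart and full dose, are not stated correctly as rules anywhere. The conclusion assumes that g/dL was intended, which every other haemoglobin limit compared here supports. The severity is minor: the intent is easy to infer and other safeguards exist. There is no effect on sample size, power or the primary analysis, and the SAP repeats no dose-modification rule.

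**What to change.** In the haemoglobin subsection of Appendix 5, replace mg/dL with g/dL in three places:

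- mandatory interruption: below 6 g/dL;
- restart at the lowest level: above 6 g/dL for 3 days;
- return to full dose: above 8 g/dL for 7 days.

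The cost is three unit corrections in one appendix, with no change to the design, sample size or analysis.
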